- The post-trial visit will occur approximately 28 days following administration of the study drug. Follow up for any clinical or laboratory adverse experiences should occur by phone or in person if the post-trial visit occurs prior to 28 days following the last dose of study drug. For confirmation of viral load return to baseline, additional data from viral load samples collected during routine follow-up visits may be transmitted to the sponsor for those participants who do not begin ART and who provide appropriate informed consent. The 672-hour sample may be collected at the post-trial visit.
- Standard meals will be provided as follows on the full PK sampling Day 1: lunch at approximately 4-hours postdose, dinner at approximately 10-hours postdose, and snacks at approximately 7-hours and 13-hours postdose. After the 24-hour postdose procedures have been completed, subsequent meals and snacks will be unrestricted in terms of caloric content, composition and timing.
- d Predose VS (HR and BP) will be collected in duplicate and Predose ECGs will be collected in triplicate within 3 hours prior to dosing MK-8527.
- e For all panels, PBMC samples may be collected up to the post-trial visit regardless of initiation of ART.
- f Analysis of viral resistance is done using NGS or Sanger technique depending on local lab.
- ^g For all panels, blood for HIV-1 viral RNA and viral resistance may be collected up to the post-trial visit if a participant does not start ART. HIV-1 RNA samples will not be collected if participants have initiated ART at 336, 504, 672 hours postdose.
- This sample should be drawn for planned analysis of the association between genetic variants in DNA and drug response. This sample will not be collected at that site if there is either a local law or regulation prohibiting collection, or if the IRB/IEC does not approve the collection of the sample for these purposes. If the sample is collected, leftover extracted DNA will be stored for FBR if the participant (or their legally acceptable representative) provides documented informed consent for FBR. If the planned genetic analyses are not approved, but FBR is approved and consent is given, this sample will be collected for the purpose of FBR.

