3 HYPOTHESES, OBJECTIVES, AND ENDPOINTS

Hypotheses are aligned with objectives in the Objectives and Endpoints table.

Study Population: Treatment naïve HIV-1 infected participants

Primary Objective	Primary Endpoint
- To evaluate the antiretroviral activity of MK-8527 in HIV-1 infected participants. - Hypothesis: At a dose that is safe and generally well tolerated, MK-8527 has antiretroviral activity, as measured by change from predose in plasma HIV-1 RNA (log10 copies/mL) at 168 hours postdose. That is, the true mean difference in the plasma HIV-1 RNA reduction from predose after MK-8527 is at least 1.0 log10 copies/mL.	- Plasma HIV-RNA (log10 copies/mL) reduction from predose
- To evaluate the safety and tolerability of MK-8527 in HIV-1 infected participants.	- Adverse events
Secondary Objectives	Secondary Endpoints
 To evaluate the intracellular PK of MK-8527-TP in PBMC after administration of single oral doses of MK-8527 to HIV-1 infected participants. Estimation: The GM C168h MK-8527-TP will be estimated 	- MK-8527-TP AUC0-168, AUC0-last, AUC0-inf, T _{max} , C _{max} , C168hr, and apparent terminal t1/2 in PBMC.
- To evaluate plasma PK of MK-8527 after administration of single oral doses to HIV-1 infected participants.	- MK-8527 plasma AUC0-last, AUC0-inf, $T_{\text{max}},C_{\text{max}},Clast,$ and apparent terminal $t1/2$
- To evaluate the PK- pharmacodynamic association of intracellular MK-8527-TP with viral load reduction.	- PK (MK-8527-TP in PBMC) / pharmacodynamic (plasma HIV-1 RNA) correlation.

PRODUCT: MK-8527 PROTOCOL/AMENDMENT NO.: 004-02

Tertiary/Exploratory Objectives	Tertiary/Exploratory Endpoints
- To evaluate the relationship between dose and antiretroviral activity of MK-8527.	- Dose-response (plasma HIV-1 RNA) relationship.
- To explore the relationship between genetic variation at response to the treatment administration and mechanisms of disease. Variation across the human genome may be analyzed for association with the clinical data collected in this study.	- Germline genetic variation and association to clinical data collected in this study

08CYXG

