4 STUDY DESIGN

4.1 Overall Design

This is an open-label, single-dose, multiple panel trial of MK-8527 in participants with HIV-1 infection. This study will be conducted in conformance with GCP.

A total of up to 4 panels (Panels A to D) will be enrolled. Panel A will consist of up to 8 participants, and Panels B, C and D will consist of up to 6 participants in each panel. In each panel, participants will receive a single oral dose of MK-8527 as outlined in [Table 1] and will undergo safety assessments and blood sampling for PK and VL analysis.

In Panel A, 8 participants were administered single 1.0 mg doses of MK-8527. In Panel B, 6 participants were administered single 0.5 mg doses of MK-8527. Panel C dose selection 0.25 mg MK-8527) follow the review of safety, tolerability, PK, and viral load data from Panels A and B through at least 10-days (240 hours) postdose.. Based on analysis of safety and antiviral efficacy in Panel C, a repeat of the 0.25 mg dose of MK-8527 may be evaluated in Panel D.

All doses of study drug intervention will be administered following at least an 8-hour fast.

Participants will be strongly encouraged to initiate an appropriate ART regimen within ~30 days of dosing MK-8527. The exact timing and regimen will be decided by the participant in consultation with the PI or their physician, but ART initiation should not occur before 10 days (240 hours) postdose in order to determine efficacy up to this time point.

All participants will be followed for safety monitoring for approximately 28 days after dosing of MK-8527. If participants start ART as planned, after the completion of the 240 hour procedures, the final blood draw for VL and viral resistance will occur on the day of ART initiation (prior to receiving the first dose of ART). If participants do not initiate ART, the Investigator may ask to continue regular blood draws for VL changes and viral resistance for up to ~28 days postdose. Participants choosing to forgo follow-on ART may also be asked if they wish to continue to participate in monitoring of VL and viral resistance beyond 28 days. Blood for MK8527-TP PBMCs will be collected throughout the study regardless of ART initiation.

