If the physician and/or Investigator believe that there is a strong indication to start ART before 10 days (240 hours) postdose this should be discussed with the Sponsor prior to starting. The initiation of follow-on ART is not a requirement for participation in the study and is ultimately a decision of the participant and the primary investigator or the participant's physician; the Sponsor will not source the ART.

Because this is a Phase 1 assessment of MK-8527 in humans, the PK, pharmacodynamic, and safety profiles of the compound are still being elucidated. This protocol is therefore written with flexibility to accommodate the inherent dynamic nature of Phase 1 clinical studies. Refer to Section 8.11.6 for examples of modifications permitted within the protocol parameters.

Specific procedures to be performed during the study, including prescribed times and associated visit windows, are outlined in Section 1.3 of the SoA. Details of each procedure are provided in Section 8.

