5.1 Inclusion Criteria

An individual is eligible for inclusion in the study if the individual meets all of the following criteria:

Type of Participant and Disease Characteristics

- 1. Other than HIV-1 infection, is in good health based on medical history, physical examination, VS measurements performed at the prestudy (screening) visit and/or prior to administration of the single dose of study drug.
- 2. Is documented HIV-1 positive as determined by a positive ELISA or QT-PCR with confirmation (eg, Western Blot).
- 3. Has a screening plasma HIV-1 RNA \geq 5,000 copies/mL within 30 days prior to the treatment phase of this study.
- 4. Has a screening plasma CD4+ T-cell count of >200/mm3.
- 5. Is ART-naïve, which is defined as not having received any marketed antiretroviral agent for the treatment of HIV-1 infection. Previous use of an antiretroviral agent for PrEP or as an investigational treatment is permitted if the most recent administration of the previous agent was at least 30 days prior to study drug administration.
- 6. Is willing to receive no other ART for the monitoring period of this study.
- 7. Has no evidence at screening for mutations conferring resistance to NRTIs (including but not limited to M184V, M184I) as previously defined.
- 8. Has the following laboratory values at screening: direct bilirubin ≤ 1.0 mg/dL, AST (SGOT) and ALT (SGPT) ≤ 2 x upper limit of normal.

Demographics

9. Is male or female, from 18 years to 60 years of age inclusive, at the time of providing informed consent

Male Participants

10. If male, agrees to the following during the intervention period and for at least 8 weeks after the last dose of study intervention:

Abstains from heterosexual intercourse as their preferred and usual lifestyle (abstinent on a long-term and persistent basis) and agrees to remain abstinent OR

Uses contraception unless confirmed to be azoospermic (vasectomized or secondary to medical cause, documented from the site personnel's review of the participant's medical records, medical examination, or medical history interview) as detailed below:

- Uses a male condom plus partner use of an additional contraceptive method when having penile-vaginal intercourse with a WOCBP who is not currently pregnant. Note: Men with a pregnant or breastfeeding partner must agree to remain abstinent from penile-vaginal intercourse or use a male condom during each episode of penilevaginal penetration.

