All participants will be encouraged to initiate ART within one month after their dose of MK 8527 but not before 10 days (240 hours) postdose. This timing is required to gather full efficacy data for this novel long-acting anti-retroviral compound and is consistent with prior anti-retroviral monotherapy PoC trials, in which low-dose anti-retroviral monotherapy has been administered for as long as 28 days and with EMA guidance [European Medicines Agency 2016]. The exact timing of ART initiation and regimen will be decided by the participant in consultation with PI/his/her physician, If the physician and/or Investigator believe there is a strong indication to start ART before Day 11, this should be discussed with the Sponsor prior to starting, as with other concomitant medications (see above).

COVID-19 vaccine may be administered until 72 hours prior to the initial dose of study drug and/or starting from 48 hours after the last dose of study drug.

6.5.1 **Rescue Medications and Supportive Care**

No rescue or supportive medications are specified for use in this study.

6.6 **Dose Modification (Escalation/Titration/Other)**

Prior to each intervention, the clinical and laboratory safety data, and VL data from the previous dose level will be reviewed by the investigator and discussed with the Sponsor to permit a decision on whether to advance to the next dosing level. No dose modification will occur without the joint agreement of the investigator and the Sponsor.

Dose selection for Panel B were made jointly by the investigator and the Sponsor. Dose escalation decision occurred after VL data from at least 5 evaluable participants were available from Panel A. The dose for Panels C and D were based on the review of all safety and VL data from participants in Panels A and B.

The decision to conduct Panel D will be made jointly by the investigator and the Sponsor, and will occur after VL data from Panel C is available.

Dose escalation decisions will be based on key safety data including VS, 12-lead ECGs, laboratory safety tests, and AEs from the previous dose levels up to at least 240 hours. See Section 4.3. If, as judged by the Sponsor and investigator, the safety and tolerability data do not justify dose escalation, the dose will not be increased as planned. Instead, participants may:

- receive the same dose level to further evaluate that particular dose level;
- receive a lower dose of the study intervention;

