8.11.5 Critical Procedures Based on Study Objectives: Timing of Procedure

For this study, the VL and PBMC blood sample for MK-8527 are the critical procedures.

At any postdose time point, the PBMC blood sample for MK-8527 needs to be collected as close to the exact time point as possible. All other procedures should be completed as close to the prescribed/scheduled time as possible. Study procedures can be performed prior or after the prescribed/scheduled time.

The order of priority can be changed during the study with joint agreement of the investigator and the Sponsor Clinical Director.

Any nonscheduled procedures required for urgent evaluation of safety concerns take precedence over all routine scheduled procedures.

The following variance in procedure collection times will be permitted.

• PK Collection (MK-8527 plasma and MK-8527-TP PBMC) and pharmacodynamic collection (viral load) as outlined in [Table 5].

PK Collection	PK Collection Window
0 to <1 h	5 min
1 to <2 h	10 min
2 to <24 h	15 min
24 to <48 h	1 h
48 to <96 h	2 h
96 to 168 h	4 h
>168 to <672 h	24 h
672 h	48 h

Table 5 Pharmacokinetic (Blood) Collection Windows

- Predose standard safety evaluations: VS and ECG up to 3 hours; laboratory safety tests and physical exam up to 24 hours
- Postdose standard safety evaluations: VS, ECG, laboratory safety tests, and physical exam
 - <24 hours postdose may be obtained within 15 min of the theoretical sampling time
 - 24 hours to <48 hours postdose may be obtained within 1 hour of the theoretical sampling time
 - 48 hours to <96 hours postdose may be obtained within 2 hours of the theoretical sampling time
 - 96 hours to 168 hours postdose may be obtained within 4 hours of the theoretical sampling time
 - >168 hours to <672 hours postdose may be obtained within 24 hours of the theoretical sampling time
 - 672-hours postdose may be obtained within 48 hours of the theoretical sampling time

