9.6 Statistical Methods

Primary (Pharmacodynamics)

The log10 plasma HIV-RNA (copies/mL) measurements from participants in all panels will be pooled and analyzed based on a longitudinal data analysis (LDA) model containing fixed effects for dose level, time (predose, 168 hours postdose) and dose level by time interaction, and a random effect for participant. The response vector consists of the baseline and 168 hours post-baseline values. Time is treated as a categorical variable so that no restriction is imposed on the trajectory of means over time. The change from baseline for each dose level at 168 hours post-baseline will be estimated from this model. A posterior distribution for the true mean change from baseline at 168 hours will be generated for each dose level using flat priors under a normal likelihood assumption.

Using the posterior distributions for each dose level the posterior distribution of the true mean will be generated, and the posterior probability that the true mean in the log10 plasma HIV-1 RNA reduction from baseline of MK-8527 is at least 1.0 log10 copies/mL will be calculated.

A 70% posterior probability for at least one dose level that also exhibits an acceptable safety and tolerability profile will satisfy the primary pharmacodynamics hypothesis. To address the exploratory objective related to antiretroviral activity at 672 hours post-baseline, a similar analysis will be performed using VL measurements at baseline and 672 hours post-baseline. Similar exploratory analyses may be performed at timepoints earlier than 168 hours postbaseline.

Primary (Safety)

Incidence of AEs will be descriptively summarized. Summary statistics and plots will be generated for the change from baseline values in the VS, ECG parameter values, and selected laboratory safety parameter values for participants, as deemed clinically appropriate. Depending on the safety parameter, the difference from baseline will either be computed on the original scale (raw change from baseline) or on the log scale and back-transformed for reporting (percent change from baseline). Summary statistics for the raw laboratory safety tests, ECGs, and/or VS may also be computed, as deemed clinically appropriate.

Secondary (Pharmacokinetic)

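### The exploratory 672-hour viral-load analysis uses only predose and 672 h values although HIV RNA sampling ends at ART start; its estimate is biased if ART start depends on post-dose viral load

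*Combined protocol and SAP*

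**What the plan says.** Section 9.6 defines the primary model with two values per participant, predose and 168 h, with dose, time, dose by time and a random participant effect. For 672 h it adds that "a similar analysis will be performed using VL measurements at baseline and 672 hours post-baseline". It attributes this to an exploratory objective at 672 h. The nearest one in Section 3 is "To evaluate the relationship between dose and antiretroviral activity of MK-8527", which names no time point.

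Sampling after ART start is limited. Section 1.3, footnote g: "HIV-1 RNA samples will not be collected if participants have initiated ART at 336, 504, 672 hours postdose". Section 4.1: "the final blood draw for VL and viral resistance will occur on the day of ART initiation", before the first ART dose. Section 8.11.5 sets sampling windows for "PK Collection (MK-8527 plasma and MK-8527-TP PBMC) and pharmacodynamic collection (viral load) as outlined in" Table 5, which allows 48 h at 672 h.

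ART is not to start before 240 h. After that the participant decides with the investigator or physician (Sections 4.1 and 6.5). The passages on uptake pull in different directions:

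- Section 6.5: "All participants will be encouraged to initiate ART within one month after their dose of" MK-8527. Section 4.1 speaks of about 30 days.
- Section 4.1: "The initiation of follow-on ART is not a requirement for participation in the study".
- Inclusion criterion 6: "Is willing to receive no other ART for the monitoring period of this study".

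Section 4.2.1.3 accepts that viral load through 28 days is assessed only in participants who do not start ART. Section 9 does not carry this into the 672 h analysis. Section 9.5 has excluded values listed in the study report, but gives no rule for values never collected because ART had begun. Section 9.6 also plans individual plots over time and permits exploratory fits.

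**The concern.** A likelihood model copes with missing outcomes when missingness depends only on values in the model. Here the only such value is the predose viral load. If a participant starts ART because viral load is rebounding at 336 or 504 h, the values that show this are outside the model, and the 672 h mean is carried by those who rebounded least. If the better-suppressed start first, the error reverses.

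At stake is how a per-dose mean, and a posterior probability of at least a 1.0 log10 reduction, will be read as evidence of how long a single dose works. Nothing in the trial acts on the 672 h result, but Section 4.2 says the study's data will aid dose selection in future studies.

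**Working it through.** **No plan figure to reproduce.** Section 9.9 gives power for 168 h only and does not enter this point. The documents state no ART uptake, so the shares below are assumptions.

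**Timing.** 672 h / 24 = 28 days, just before the target of about 30 days. Full compliance with the encouragement could leave few or nearly all participants off ART at 672 h.

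**How many values remain.** With n participants and a share p off ART, P(at most 2 values) is binomial. For n = 6, p = 0.4: 0.6^6 + 6(0.4)(0.6^5) + 15(0.4^2)(0.6^4) = 0.047 + 0.187 + 0.311 = 0.54.

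| Off ART at 672 h | n = 6 | n = 8 | n = 12 (0.25 mg, Panels C and D) |
|---|---|---|---|
| 80% | 2% | 0.1% | 0% |
| 60% | 18% | 5% | 0.3% |
| 40% | 54% | 32% | 8% |
| 20% | 90% | 80% | 56% |

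**Size of bias, large samples.** All inputs are assumed. Mean change is -1.3, -1.1, -0.7 and -0.3 log10 at 240, 336, 504 and 672 h. The SD is 0.6 for participant level, 0.45 for participant change and 0.2 for noise. After 240, 336 and 504 h, the log-odds of starting ART are a + slope x observed change, with a set to give the share off ART. Slope 1 multiplies the odds by e^1 = 2.7 per log10, and slope 3 by e^3 = 20. The planned two-point random-intercept model then estimates (true value -0.30):

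| Off ART at 672 h | Timing unrelated | Slope 1, rebound prompts ART | Slope 3, rebound prompts ART | Slope 3, better-suppressed start first |
|---|---|---|---|---|
| 90% | -0.30 | -0.32 | -0.36 | -0.24 |
| 70% | -0.30 | -0.38 | -0.46 | -0.14 |
| 40% | -0.30 | -0.46 | -0.64 | +0.04 |

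At 90 to 40% off ART the bias is thus 0.02 to about 0.17 with slope 1 (0.16 or 0.17 at 40%, depending on the run) and 0.06 to 0.34 with slope 3. With slope 1 reversed, the shift is about as large in the other direction. Counting ART-day draws inside the 48 h window moves the rebound figures slightly towards the truth.

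**What the omitted values add.** A separate large-sample calculation assumed a true 672 h reduction of 0.50, SD 0.43 for the change (Section 9.9), baseline SD 0.5, odds of ART start x4 per SD of the driving viral load, correlation 0.3 to 0.8 between the 336 and 672 h changes, and 25 to 75% on ART.

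- Start driven by 336 h viral load: the two-point random-intercept model gives 0.55 to 0.78; adding the 336 h value gives 0.50.
- Start driven by baseline only: an unstructured two-point model gives 0.50. The random-intercept version gives 0.54 to 0.64, because its equal-variance assumption fails.
- Start unrelated to viral load: all give about 0.50.

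**The proposed model under the first set of inputs (slope 3).** On predose and 168 to 672 h values it gives -0.30 at 70, 40 and 20% off ART in large samples. With a participant effect on level only, it gives -0.33/-0.37/-0.41 (rebound) and -0.27/-0.23/-0.20 (better-suppressed first). At n = 6 and 40% off ART its root mean squared error is 0.24. The two-point model has 0.45 (rebound), 0.38 (unrelated) and 0.47 (better-suppressed first).

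**The case against.** **The protocol already says that late viral load is off-ART data.** It does, in Section 4.2.1.3 and footnote g. A reader might infer that the plan hides the restriction; it does not. What is missing is its consequence in Section 9.6.

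**The result is not shown to be biased.** Correct. It is tempting to conclude that the 672 h estimate is wrong, or that any dependence of ART timing on viral load makes it so. The documents support neither reading. They report no link between timing and viral load, and dependence on baseline alone need not bias a correctly specified two-point model. The remark in Section 4.2 that ART start will not depend on screening results concerns resistance testing, so it does not rule out a link.

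**ART starters do not all lose their 672 h value.** A start within 48 h of 672 h can still supply one. Conversely, the per-protocol definition counts availability of measurements, so an early starter might not contribute even a baseline.

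**The sizes are chosen.** The slope of 3 is steep, and loss may be small if criterion 6 governs. At 90% off ART the bias is only 0.02 to 0.06.

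**The proposed model is favoured by construction.** The first simulation generates data in the form that this model assumes. When individual differences widen over time (40% off ART, n = 12, amount of widening assumed), it gives -0.45 and -0.15 against -0.71 and +0.14 for two points. Bias falls but does not vanish. The separate calculation did not use that form and points the same way.

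**Plots and exploratory fits exist.** They help interpretation, but they do not correct the planned estimate, and the fits are optional.

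**Conclusion.** The point holds as a conditional one. The 672 h values come only from participants still off ART or with an ART-day draw inside the window, and the planned model omits the values that could explain who they are. Bias follows if ART start depends on post-dose viral load. Under the stated assumptions it is about 0.02 to 0.17 log10 with moderate dependence and 0.06 to 0.34 with strong dependence, at 90 to 40% off ART and a true change of -0.30. If timing is unrelated to viral load, only precision suffers. If nearly everyone is off ART at 672 h, the matter is minor.

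A reader might extend this to the trial's main conclusion. The documents do not support that: the hypothesis is at 168 h, panel decisions use data through 240 h, and ART is not to start before 240 h. This is a cheap improvement to an exploratory analysis.

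**What to change.** In Section 9.6:

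1. Report beside the 672 h result, by dose, the number still off ART at 336, 504 and 672 h and the ART-start times. Label the result exploratory and conditional on ART start depending only on observed viral loads.
2. Replace the two-point model with one repeated-measures model on the pre-ART values at predose, 168, 240, 336, 504 and 672 h, all listed in Section 9.4. Use dose, categorical time and dose by time, with a participant effect on level and, if estimable, on change from predose. Count an ART-day draw at the scheduled visit whose Table 5 window contains it; otherwise show it in the plots. Where a dose has no 672 h value, show individual plots only.

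State also which objective the 672 h analysis serves. Separately, inclusion criterion 6 and the encouragement to start ART in Sections 4.1 and 6.5 must be reconciled.

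The cost is SAP wording and slightly more modelling on viral loads already being collected. The variance structure may be hard to estimate with 6 to 12 participants per dose. Bias is reduced, not removed, if individual differences widen over time or ART start depends on unobserved factors. Item 1 is worth adopting even if item 2 is not.
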